13.9 Communicable Disease Reporting

Study staff will comply with local requirements to report communicable diseases including HIV-1 identified among study participants to health authorities. Participants (or other authorized guardians if applicable) will be made aware of reporting requirements during the informed consent process.

13.10 Management of Incidental Findings

Site clinicians will inform participants (or other authorized guardians if applicable) of clinically meaningful physical exam findings and laboratory test results, including results of HIV tests. Participants will not receive PK test results. When applicable, site clinicians will provide referrals to non-study sources of medical care for further evaluation and/or treatment of these findings.

13.11 Management of New Information Pertinent to Study Participation

Participants (or other authorized guardians if applicable) will be provided any new information learned over the course of the study that may affect their willingness to participate and/or remain in the study or their willingness to allow their children to participate and/or remain in the study.

13.12 Post-Study Access to Study Drug

Participants will complete the study drug regimen prior to exiting the study. Therefore, post-study access to study drug is not applicable.

14 ADMINISTRATIVE PROCEDURES

14.1 Regulatory Oversight

This study is sponsored by the National Institute of Allergy and Infectious Diseases (NIAID), *Eunice Kennedy Shriver* National Institute of Child Health and Development (NICHD), and National Institute of Mental Health (NIMH), which are part of the United States National Institutes of Health (NIH). The study drug rifapentine (RPT) is provided by Sanofi; however, this organization is not involved in sponsorship or regulatory oversight of this study.

The Division of AIDS (DAIDS) within the NIAID is responsible for regulatory oversight of this study and holds the Investigational New Drug (IND) application under which the study will be conducted. DAIDS will distribute safety-related information pertaining to the study products prior to and during the conduct of the study in accordance with its sponsor obligations.

NIAID and NICHD provide funding to the clinical research sites at which this study will be conducted. Each institute contracts with independent clinical site monitors who will perform monitoring visits as described in Section 12. As part of these visits, monitors will inspect study-related documentation to ensure compliance with all applicable US and local regulatory requirements.

14.2 Protocol Registration

Prior to implementation of this protocol and prior to any subsequent full version amendments, each site must have the protocol and the protocol informed consent form approved, as appropriate, by their local IRB/EC and any other applicable regulatory entity (RE). Upon receiving final approval, sites will submit all required protocol registration documents to the DAIDS Protocol Registration Office (DAIDS PRO) at the Regulatory Support Center (RSC). The DAIDS PRO will review the submitted protocol registration packet to ensure that all of the required documents have been received.

Site-specific ICFs will be reviewed and approved by the DAIDS PRO and sites will receive an Initial Registration Notification from the DAIDS PRO that indicates successful completion of the protocol registration process. A copy of the Initial Registration Notification should be retained in the site's regulatory files.

For any future protocol amendments, upon receiving final IRB/EC and any other applicable regulatory entity approvals, sites should implement the amendment immediately. Sites are required to submit an amendment registration packet to the DAIDS PRO at the RSC. Site-specific ICFs will not be reviewed and approved by the DAIDS PRO, and sites will receive an Amendment Registration Notification from the DAIDS PRO that indicates successful completion of the amendment protocol registration process. A copy of the final amendment Registration Notification issued by the DAIDS PRO should be retained in the site's regulatory files.

For additional information on the protocol registration process and specific documents required for initial and amendment registrations, refer to the current version of the DAIDS Protocol Registration Manual, which is available on the RSC website: <http://rsc.tech-res.com/protocolregistration/>.

14.3 Study Implementation

This study will be conducted in accordance with the protocol, international good clinical practice guidelines, and all applicable US and local regulations. Study implementation will also be guided by the study-specific MOP, LPC, and other study implementation materials, which will be available on the IMPAACT web site: www.impactnetwork.org.

Study implementation at each site will also be guided site SOPs. The DAIDS policy on Requirements for Manual of Operational specifies the minimum set of SOPs that must be established at sites conducting DAIDS-funded and/or -sponsored clinical trials (available on the website referenced in Section 11.2). These SOPs should be updated and/or supplemented as needed to describe roles, responsibilities, and procedures for this study.

14.4 Protocol Deviation Reporting

Per the policy for Requirements for Source Documentation in DAIDS Funded and/or Sponsored Clinical Trials (available at the website referenced in Section 11.2), all protocol deviations must be documented in participant research records. Reasons for the deviations and corrective and preventive actions taken in response to the deviations should also be documented.

Deviations should be reported to site IRBs/ECs and other applicable review bodies in accordance with the policies and procedures of these review bodies. Serious deviations that are associated with increased risk to one or more study participants and/or significant impacts on the integrity of study data must also be reported within IMPAACT, following procedures specified in the IMPAACT Manual of Procedures.

14.5 Critical Events Reporting

Per the DAIDS policy on Identification and Classification of Critical Events, a critical event is defined as an unanticipated study-related incident that is likely to cause harm or increase the risk of harm to participants or others or has a significant adverse impact on study outcomes or integrity. All such events must be reported following procedures specified in the DAIDS Critical Events Manual, which is available at:

<http://www.niaid.nih.gov/LabsAndResources/resources/DAIDSClinRsrch/Pages/Safety.aspx>

14.6 ClinicalTrials.gov

This protocol is not subject to the Food and Drug Administration Amendments Act of 2007 (FDAAA); however, it will be registered in <https://clinicaltrials.gov/> to meet International Committee of Medical Journal Editors (ICMJE) requirements.

15 PUBLICATIONS

All presentations and publications of data collected in this study are governed by IMPAACT policies, which are available in the IMPAACT Manual of Procedures.

Appendix I-A: Mother Schedule of Evaluations

	SCR (up to 2 weeks prior to entry)	Entry/Intensive PK Sampling (Days 0-3)	Weekly (7 ± 2 days apart) (weeks 1-12)	Monthly (Every 4 weeks ±2 weeks) (until 24 weeks after delivery)	Study Exit/ Early Discontinuation
Administrative and Regulatory					
Obtain written informed consent	X				
Assign participant identification numbers (PIDs) to mother and infant	X				
Obtain screening number from SES	X				
Complete eligibility checklist and enter into SES		X			
Assign separate study identification numbers to mother and infant		X			
Assess eligibility	X	X			
Provide meal prior to administering study drug		X	X		
Behavioral and Counseling					
Provide HIV pre-/post-test counseling if applicable	X				
Assess alcohol and drug use	X				
Signs and symptoms of active TB Counseling		X	X	X	X
Assess infant feeding methods (postpartum only)			X	X	
Clinical					
Obtain/update medical and medications history	X	X	X	X	X
Perform physical examination	X	X	X	X	X
Perform obstetrical exam/assess fetal movement and heart sounds (until delivery)	X	X	X	X	
Perform ultrasound	X				
Provide available findings/test results		X	X	X	X
Assess TB symptoms, risk, and exposure	X	X	X	X	X
Gene Xpert, shielded chest x-ray, or sputum microscopy	X				
Record/update AEs		X	X	X	X
TST (if not available per medical record)	X				
Study Product					
Prescribe and administer DOT of study drug regimen		X	X		

Laboratory					
IGRA (3mL) (if not available per medical record)	3mL				
Complete blood count (CBC)	3mL		3mL (every 4 weeks)	3mL	
Liver Function tests	3mL		3mL (every 4 weeks)	3mL	
HIV-1 test (confirmatory tests as needed)	6mL				
CD4 count (HIV-1-infected only)		3mL			
Coagulation profile	5mL		5mL (at one visit at ≥ 34 weeks gestational age only)	5mL (if clinically indicated)	
HBsAG, HBsAb, HCV Ab		6mL			
Intensive PK sample collection		22mL			
Sparse PK sample collection			8mL (last dose)		
Plasma sample collection (breast milk PK eligible only)			24mL (first and second week postpartum)		
Breast milk PK sample collection (if eligible)			X (first and second week postpartum and last dose)		
TOTAL BLOOD	17-20mL	28-31mL	11-43mL	6-11mL	

Appendix I-B: Infant Schedule of Evaluations

	Newborn Visit (within 3 days of life)	Monthly (Every 4 weeks \pm 2 weeks) (until 24 weeks after delivery)	Study Exit/Early Discontinuation
Clinical			
Assess eligibility for single PK sampling	X		
Physical exam	X	X	X
Record/update medical and medications history	X	X	X
Record/update AEs	X	X	X
Provide available test results to mother	X	X	X
Assess TB symptoms, risk and exposure		X	X
Laboratory			
Single PK sample collection (if eligible)	2mL		
Coagulation profile (if eligible)	2mL	2 mL (if clinically indicated)	
Complete blood count (if clinically indicated)		1mL	
Liver Function Test (if clinically indicated)		2mL	
Cord blood (optional if eligible, during mother's delivery)	X		
TOTAL BLOOD	2-4mL	1-5mL	

Appendix II: Modeling and Simulation Population Analysis Report – Rifapentine

This population pharmacokinetic (PK) analysis estimates the pharmacokinetics of rifapentine (RPT) and its main metabolite 25-desacetyl-rifapentine (25-des-RPT) based on the combined dataset from 4 clinical studies in children, healthy adolescents and adult patients with active or latent tuberculosis infection (LTBI) where rifapentine was administered either as a single dose or weekly: two Phase I clinical studies (children, adolescents) (63, 64), one Phase I/II clinical study (TBTC Study 25) (65) and one Phase III clinical study (TBTC Study 26) (25).

The population PK analysis comprised a total of 1634 rifapentine and 25-desacetyl-rifapentine serum concentrations from 227 children, adolescents and patients with active or latent tuberculosis who received a range of 300-1200 mg oral doses of rifapentine as a single agent (children, adolescents), or in combination with isoniazid (INH) in TBTC Study 25 and TBTC Study 26. Serum concentration data of RPT and 25-des-RPT were modeled simultaneously using a population analysis approach to estimate RPT and 25-des-RPT population PK parameters (mean and inter-patient variability) as well as the relationship between PK parameters and covariates.

The structural model that best described the pharmacokinetics of rifapentine was a 1-compartment model with a transit compartment chain for description of the absorption delay. All clearance and volume of distribution parameters were allometrically scaled using standard exponents (e.g. 0.75 for clearance and 1 for volume). The following typical population estimates (%RSE) of rifapentine pharmacokinetics were obtained: oral clearance (CL/F) for 70kg patient 2.32 L/h (11 %); central volume of distribution (Vc/F) for 70 kg patient 51.7 L (10 %); absorption rate constant (k_a) 1.69 (34) h⁻¹, mean transit time (MTT) 0.62 h (27) and number of transit compartments (n) 1.8 (76). The inter-patient variability was 40% (13 %) for CL/F, 47% (15 %) for V/F and 90% (47 %) for MTT.

The structural model that best described the pharmacokinetics of 25-des-RPT was a 1-compartment model. The typical population estimates (%RSE) of 25-des-RPT apparent clearance (CL_m/F_m) and apparent volume (V_m/F_m) for 70kg patient were 2.05 L/h (10 %) and 21.9 L (7 %), respectively. The inter-patient variability was 64% (18 %) for CL_m/F_m.

Apparent clearance per kilogram body weight was significantly higher in children than adults. This relation was described by a maturation function, where clearance for the youngest child (age, 2 y) was 0.052 L/h/kg, decreasing to the fully matured value of 0.026 L/h/kg by older age (half-life, 1.5 y (38% RSE), resulting with fully matured value by approximately age 10). Relative bioavailability of rifapentine in fasting condition for higher doses, 900 mg and 1200mg compared to the lowest available dose in adults (600 mg) was found to be 0.96 (19% RSE) and 0.76 (16% RSE) respectively. Food increased relative bioavailability by 40% (8% RSE). Children who received crushed tablets had 26% (36% RSE) decreased relative bioavailability. There was no autoinduction with once-weekly dosing. Gender and race have also been investigated, and were not associated with rifapentine pharmacokinetics.

SUMMARY OF STUDY FEATURES

This population PK analysis evaluated data obtained from 4 clinical studies of rifapentine (TBTC Study 25, TBTC Study 26, children and adolescent study) (25, 63-65). A summary of the studies is provided in Table 1. PK profiles from a total of 227 subjects were used in this analysis.

Table 1. Summary of Studies Included in the Population PK Analysis

Study	Phase	n ^a	Population	Treatment	DrugX Dose
TBTC 25	I/II	35	Adult Patients with TB	RPT+INH	600mg, 900mg, 1200mg weekly
TBTC 26	III	157	Children and Adults with LTBI	RPT + INH	300- 900mg weekly
children	I	23	Children w/o TB	RPT	150mg, 300mg single dose
adolescent	I	12	Healthy Adolescents	RPT	450mg, 600mg single dose

^a Number of subjects receiving RPT included in the population PK analysis

TBTC Study 25

TBTC Study 25 was a prospective, double-blind, randomized Phase II trial to evaluate the tolerability of once-weekly, continuation phase, directly observed therapy with rifapentine at three doses (600, 900, and 1,200 mg) and of isoniazid in 150 HIV-seronegative patients with drug susceptible tuberculosis. The pharmacokinetic substudy included 35 adult patients with tuberculosis (continuation phase therapy) who received commercial formulation of rifapentine (600, 900, or 1200 mg once weekly), usually without food. Pharmacokinetic data were collected after ≥ 3 weeks of once-weekly treatment. Plasma samples for rifapentine and metabolite concentrations were collected (11 samples: baseline, 2, 4, 6, 8, 10, 12, 18, 24, 48, and 72 h after the dose) (65, 66).

TBTC Study 26 (PREVENT-TB Study)

TBTC Study 26 was a Phase 3, randomized treatment trial of 8,053 patients with LTBI, comparing a 12-dose, once-weekly rifapentine and isoniazid regimen (3HP) to nine months of daily isoniazid (25). 161 patients were recruited into PK substudy from the Phase 3, PREVENT TB trial, of whom 157 had evaluable PK samples (80 children and 77 adults). Risk groups in the treatment trial were recent close contacts of pulmonary tuberculosis cases, HIV-infected persons, those with a recent tuberculin skin test conversion, or those with fibrotic or fibronodular abnormalities consistent with old, healed tuberculosis on chest radiograph. All patients had evidence of latent tuberculosis infection (e.g. positive tuberculin skin test) and no evidence of active tuberculosis. Children enrolled in this substudy were age 2 to 11 years and all children and adults in the PK substudy were treated with 3HP. Rifapentine was administered as 150 mg tablets. Rifapentine doses in children ranged from 300 to 900 mg based on weight and dosage (Table 2) and the rifapentine dose in adults was 900 mg (all patients weighed more than 45 kg). Children who could not swallow tablets were administered a suspension of crushed rifapentine and isoniazid tablets in either a soft food or liquid. Other foods consumed within two hours of drug administration were documented. For children, the once-weekly dosage of isoniazid was 25 mg/kg, (900 mg maximum), and adults were administered isoniazid 15 mg/kg (900 mg maximum) (25).

Table 2. Rifapentine dosing algorithm used for children in the PREVENT-TB study

Weight (kg)	Rifapentine dose (mg)	Rifapentine dosage (mg/kg)	Number of children in each group	Age of study patients (mean +SD in years)
10-14	300	21-30	34	2.6 \pm 0.8
>14-25	450	18-32	40	4.5 \pm 1.6
>25-32	600	19-24	7	7.4 \pm 2.2
>32-50	750	15-23	16	9.7 \pm 2.4
>50	900	<18	3	10.0 \pm 1.0

After at least three once-weekly doses of rifapentine and isoniazid, a single plasma sample collected 24-hours after administration of study drugs (C24) was used in the sampling protocol. A 2 mL venous blood sample for PK analysis was obtained 23 to 25 hours after drug administration and was processed according to standard procedures (67). Plasma concentrations of rifapentine and 25-des-RPT were determined using a validated high-pressure liquid chromatography assay (66).

Children study

The pharmacokinetic study in children included 23 children (age, 2 to 12 y) without tuberculosis. The children received rifapentine tablets (150 or 300 mg) without food. If a child had difficulty swallowing tablets, the tablets were crushed before administration (that was the case in 9 out of 23 children). Plasma samples for rifapentine and metabolite concentrations were collected (11 samples: before the dose and 0.5, 1, 2, 3, 4, 6, 10, 12, 24, and 32 h after the dose) (64).

Adolescent study

The pharmacokinetic study in adolescents included 12 healthy subjects (age, 12 to 15 y) who received rifapentine (1 dose; 450 mg for adolescents weighing < 45kg or 600 mg for adolescents weighing >45 kg) without food. Plasma samples for rifapentine and metabolite concentrations were collected (11 samples: before the dose and 2, 3, 4, 5, 6, 8, 12, 24, 48, and 72 h after the dose) (63).

IMPAACT 2001

Final Pharmacokinetic Statistical Analysis Plan

**A Phase I/II Trial of the Pharmacokinetics, Tolerability, and Safety of Once-Weekly Rifapentine and Isoniazid in HIV-1-infected and HIV-1-uninfected Pregnant and Postpartum Women with Latent Tuberculosis Infection
Protocol Version 1.0**

ClinicalTrials.gov Identifier: NCT02651259

P2001 PHARMACOKINETIC ANALYSIS PLAN

OBJECTIVES

Primary

Pharmacokinetic (PK, concentration-time) data and safety data of rifapentine (RPT) and desacetyl-rifapentine (des-RPT, metabolite) in pregnant women

Secondary

PK data of RPT and des-RPT in postpartum women and infants; PK data of isoniazid (INH) in pregnant and postpartum women

DATA

Dataset checking

Source datasets provided to UCSF will be checked by IMPAACT against the original database. Datasets may need to be subsequently manipulated during the PK analysis. Each time manipulations are performed the new dataset will be checked against the original dataset. The following checks will be performed:

- Comparison of number of subjects in the new dataset to those expected to be retained from the initial dataset
- Number of observations per subject in the new dataset to those expected to be retained from the initial dataset
- Check of dosing history (PK sampling times relative to dosing, missing dosing or sampling times).

Any discrepancies/errors found in the dataset will be corrected and documented.

Exclusion of data points

All evaluable data will be used for analysis. All data exclusions will be documented.

Identification of outliers

Individual data points that are clearly aberrant and/or with residuals (weighted, conditional weighted, and/or individual weighted) greater than 6 will be considered for omission. An assessment of their impact on the analysis will be documented.

Handling of missing data

The population median value at each time point may be used for missing data from a continuous variable (e.g. age, weight, and serum creatinine level) for a particular subject. If any value is missing at baseline, screening values may be used for imputation, if available.

METHODOLOGY

RPT and des-RPT

Adults

Approach

Population-based estimates of PK parameters for RPT (CL/F, absorption, volume of distribution) and des-RPT (CL_{metabolite}/F) will be derived for

- (1) pregnant women in the second and third trimesters of pregnancy and
- (2) women after delivery (postpartum).

Secondary PK parameters for RPT and des-RPT (area under the curve (AUC), maximum concentration (C_{max}), and minimum concentration (C_{min})) will be derived from the model for pregnant women in the second and third trimesters of pregnancy.

P2001 PHARMACOKINETIC ANALYSIS PLAN

The study data, which provide a mix of longitudinal and cross-sectional observations, will be combined and modeled using nonlinear mixed effects approaches that are widely used in pharmacology research. Nonlinear mixed effects modeling will be performed using NONMEM v7.4. Dataset manipulation and data visualization will be performed using R v3.5.1 and Microsoft Office Excel. Perl-speaks-NONMEM (PsN) v4.8.1 and Xpose4 v4.6.1 will be used for model evaluation.

Exploratory data analysis

Prior to beginning modeling analyses, the following exploratory data analyses will be performed:

- Scatterplots of dependent variable (DV) versus time, stratified by treatment outcome, cohort, or disease status
- Summary statistics including the number of patients, samples, samples per patient, and number of patients with samples at each visit.

Structural model development

The absorption and disposition kinetics of RPT and des-PRT will be described by a one compartment model with first-order (linear) elimination and first-order oral absorption. More complex models with respect to absorption (e.g. transit compartments), distribution, and elimination will be explored if necessary.

Goodness-of-fit diagnostic plots will be used to assess the structural model:

- Observations versus population and individual predictions
- Population, individual, and conditional weighted residuals versus time

Stochastic model development

Exponential error models will be used to characterize the between-subject-variability of the model parameters. A diagonal sigma-structure will be used, and off-diagonal elements may be included.

For continuous data, additive, proportional, and combined (additive and proportional) error models will be used to characterize the residual variability.

The appropriateness of the random error models will be assessed using diagnostic plots:

- Observations versus population and individual predictions
- Population, individual, and conditional weighted residuals versus time
- Observations versus time with population and individual fits
- Histogram of ETA estimates

Model evaluation

Visual predictive checks will be used to evaluate how well the model describes the data.

Infants

Approach

Summary statistics will be compiled for plasma and cord blood RPT and des-RPT concentrations in infants collected within 72 hours following birth.

Dataset manipulation and data visualization will be performed using R v3.5.1 and Microsoft Office Excel.

Summary statistics

P2001 PHARMACOKINETIC ANALYSIS PLAN

Cord blood and plasma concentration data for RPT and des-RPT will be summarized by

- Count
- Minimum concentration and maximum concentration
- Mean and median
- First quantile and third quantile.

INH

Adults: Approach

Population-based estimates of PK parameters for INH (CL/F, absorption, volume of distribution) will be derived for all pregnant women irrespective of pregnancy trimester or pre-/post-partum status.

The study data, which provide a mix of longitudinal and cross-sectional observations, will be combined and modeled using nonlinear mixed effects approaches that are widely used in pharmacology research. Nonlinear mixed effects modeling will be performed using NONMEM v7.4. Dataset manipulation and data visualization will be performed using R v3.5.1 and Microsoft Office Excel. Perl-speaks-NONMEM (PsN) v4.8.1 and Xpose4 v4.6.1 will be used for model evaluation.

Exploratory data analysis

Prior to beginning modeling analyses, the following exploratory data analyses will be performed:

- Scatterplots of dependent variable (DV) versus time, stratified by treatment outcome, cohort, or disease status
- Summary statistics including the number of patients, samples, samples per patient, and number of patients with samples at each visit.

Structural model development

The absorption and disposition kinetics of INH will be described by a one compartment model with first-order (linear) elimination and first-order oral absorption. More complex models with respect to absorption, distribution, and elimination (e.g. mixture models) will be evaluated if necessary.

Goodness-of-fit diagnostic plots will be used to assess the structural model:

- Observations versus population and individual predictions
- Population, individual, and conditional weighted residuals versus time

Stochastic model development

Exponential error models will be used to characterize the between-subject-variability of the model parameters. A diagonal sigma-structure will be used, and off-diagonal elements may be included.

For continuous data, additive, proportional, and combined (additive and proportional) error models will be used to characterize the residual variability.

The appropriateness of the random error models will be assessed using diagnostic plots:

- Observations versus population and individual predictions
- Population, individual, and conditional weighted residuals versus time
- Observations versus time with population and individual fits
- Histogram of ETA estimates

Model evaluation

Visual predictive checks will be used to evaluate how well the model describes the data.

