6.3 Mother Weekly Visit (On Study Drug Regimen), Sparse PK Visit

Women will have weekly study visits while on the study drug regimen. Requirements for sequencing of procedures at the weekly visits are as follows:

- Before administering study drug regimen:
 - Prescribe study drug regimen per site SOP
 - Provide meal

The PK sampling visits are ideally conducted in the morning. The Sparse PK sample collection will be conducted on the visit of the woman's last dose of the study drug regimen over the course of 48 hours according to the following time points: 1h, 4h, 24h, and 48h after the observed dose. Women who are still taking study drug and breastfeeding postpartum will express breast milk, and plasma samples will also be drawn at the following time points:

- First weekly visit after delivery, three hours after the study drug dose
- Second weekly visit after delivery, six hours after the study drug dose
- Last dose visit, 24 hours after the study drug dose (breast milk collection only)

Women will be asked to refrain from eating for two hours prior to each PK sampling dose, except for the meal provided by the site, which is to be eaten within 30 minutes before study drug administration. Women will be asked to refrain from further intake (except water) until three to four hours after the dose. The food type and quantity prior to each PK sampling dose will be recorded on CRFs.

RPT PK testing will be performed on all Sparse PK samples, after which, the 1h and 4h samples will be stored for later INH PK testing (see LPC for further details).

Mother Weekly Visit Procedures (7 ± 2 days apart)		
Administrative and Regulatory		
 • Provide meal within 30 minutes prior to administering study drug
Behavioral and Counseling		
 • Signs and symptoms of active TB Counseling • Assess infant feeding methods (postpartum only)
Clinical		
 • Perform targeted physical exam • Record/update medical and medications history • Record/update AEs • Provide available test results • Assess TB symptoms, risk and exposure • Assess fetal movement and heart sounds (until delivery)

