6.7.2 Physical Examination

Maternal complete physical examination:

For women, a complete physical exam will include the following: vital signs (temperature, pulse, blood pressure, and respiration), assessment of general appearance, cardiac exam, pulmonary exam, lymph node exam, and liver and spleen size per abdominal exam. Weight (so BMI and change in weight can be calculated) and mid-upper arm circumference (MUAC) will also be measured. Height will be assessed at the Entry Visit only.

Maternal targeted physical examination:

For women, a targeted physical exam during study follow-up will include vital signs (temperature, pulse, blood pressure, and respiration) and weight. Additional assessments should be driven by any previously identified or new signs or symptoms including diagnoses that the woman has experienced since the last visit.

Infant complete physical examination:

For infants, at the Newborn Visit, a complete physical exam will include the following: APGAR scores, birth weight and length, head circumference, gestational age, congenital abnormalities, demographics.

Infant limited physical examination:

For infants, at the monthly study visits, a limited physical exam will include the following: Weight (documented on a growth chart), length, head circumference, and vital signs (temperature, heart rate, and respirations). Additional assessments should be driven by any previously identified or new signs or symptoms including diagnoses that the infant has experienced since the last visit.

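### The SAP lets a missing weight be replaced by the group median after baseline, although the woman's own recent weight will normally be on file (minor)

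*SAP*

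**What the plan says.** The SAP, under Data, Handling of missing data, has two sentences on this. The first is permissive and lists weight among its examples: "The population median value at each time point may be used for missing data from a continuous variable". The second covers baseline only: "If any value is missing at baseline, screening values may be used for imputation, if available". The SAP does not define a time point, does not rank the two rules, and gives no rule for using a woman's own measurements after baseline.

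The protocol provides many such measurements. Section 6.3 states: "Women will have weekly study visits while on the study drug regimen". Its procedure table lists "Perform targeted physical exam" for each of those visits, and section 6.7.2 says what that involves: "a targeted physical exam during study follow-up will include vital signs (temperature, pulse, blood pressure, and respiration) and weight". The complete examination, done at screening and at the monthly visits after treatment, also covers it: "Weight (so BMI and change in weight can be calculated) and mid-upper arm circumference (MUAC) will also be measured".

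Weight has a direct role in the model. Protocol section 10.5 plans allometric scaling of CL and V together with gestational-age effects, and objective 2.2.2 names weight as a covariate. Section 10.5 gives no exponents. The historical rifapentine model in Appendix II used "0.75 for clearance and 1 for volume".

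**The concern.** When a covariate is measured repeatedly, the best stand-in for a missing value is usually the same person's adjacent value. Body weight differs far more between women than it does within one woman over a week. Using the group median discards the better information and pulls heavy and light women towards the centre.

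The exposed visit is the sparse PK visit, which takes place at the last dose. Intensive PK is at the first dose, which is baseline, where the screening value is allowed. Women enter at 14 to 34 weeks, and twelve weekly doses put the last dose about 11 weeks later. That is roughly 25 weeks' gestation (14 + 11) at one end and after delivery (34 + 11 = 45 weeks) at the other. If a time point means the study visit, its median mixes pregnant and delivered women. A woman with a true weight at entry and a median at the last dose would show a false change in weight just as her pregnancy stage changes.

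**Working it through.** **1. Check the exponent against the plan's own figures.** Inputs: CL/F of 2.32 L/h at 70 kg (Appendix II); a 40% rise in bioavailability with food (Appendix II); 2.07 L/h fasting and 1.47 L/h fed for a 60 kg woman (section 10.3.2).

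- 2.32 × (60/70)^0.75 = 2.067 L/h, against 2.07 stated.
- 2.067 / 1.40 = 1.476 L/h, against 1.47 stated.

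So 0.75 is the scaling behind the protocol's own comparison value. Its use in this trial's model is an assumption.

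**2. Error in weight-predicted CL under the median rule.** Formula: (median weight / true weight)^0.75 − 1. The documents give no weight distribution, so the following is an assumption: median equal to mean, 68 kg, with SD 10, 13 or 16 kg.

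| Assumed SD | Woman 1 SD above | Error in CL | Woman 2 SD above | Error in CL |
|---|---|---|---|---|
| 10 kg | 78 kg | (68/78)^0.75 − 1 = −9.8% | 88 kg | (68/88)^0.75 − 1 = −17.6% |
| 13 kg | 81 kg | (68/81)^0.75 − 1 = −12.3% | 94 kg | (68/94)^0.75 − 1 = −21.6% |
| 16 kg | 84 kg | (68/84)^0.75 − 1 = −14.7% | 100 kg | (68/100)^0.75 − 1 = −25.1% |

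On the light side the sign reverses and the error is larger: for 55 kg, (68/55)^0.75 − 1 = +17.2%. A woman at the median has no error. If weight is lognormal with CV 15%, 20% or 25%, the median absolute error among imputed women is 7.5%, 10.0% or 12.4%.

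**3. Error if her own weight is used.** With 1 kg of difference, (69/68)^0.75 − 1 = +1.1%. At 60 to 70 kg, differences of 0.5 to 2 kg give about 0.5% to 2.4%, and 3 kg gives 3.1% to 3.6%.

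**4. Effect on the population value.** As a rough guide, one affected woman among n shifts the mean log weight-predicted CL by ln(1 + error)/n.

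- Error +22%: ln(1.22) = 0.199, so 0.4% at n = 50, 0.8% at n = 25 and 1.7% at n = 12.
- Error −21.6%: ln(0.784) = −0.243, so 0.5%, 1.0% and 2.0% in absolute size.

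Errors for heavy and light women partly cancel.

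**The case against.** The strongest reply is that the rule will rarely matter.

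- **It is permissive.** The SAP says the median may be used, so an analyst remains free to take the woman's own weight. This stands: the plan cannot be said to impose the median. It does, however, leave the choice open in a final SAP, and the better option is named only for baseline.
- **Few weights should be missing.** Every dose is given under observation at a visit that includes weighing, so a woman with sparse PK data attended such a visit. This also stands. The documents give no rate of missing weights, and nothing in them shows that gaps are commoner at the last dose.
- **Her own concentrations help.** She has up to 11 intensive and 4 sparse samples, and between-subject variability is modelled, so part of a weight error goes into her random effect rather than her estimated CL. This is partly right. The SAP names no between-occasion term, so one random effect per woman cannot fully absorb an error present only at the later visit. That matters only if weight enters as a time-varying covariate.

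A reader might infer that errors of 10-25% come close to the protocol's 25% margin and could trigger or mask a dose decision. The documents do not support this. In sections 10.3 and 10.3.2 the margin applies to the median CL/F of a cohort, and changes based on one woman's PK are excluded. The interim trigger in section 10.3.1 is completed intensive PK sampling, which is at baseline, where the screening weight, at most two weeks old, is allowed.

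**Conclusion.** The point holds as a minor one. For a missing weight after baseline the SAP names a poorer substitute and omits a better one that the protocol's visit schedule normally supplies. The place where this bears is the sparse PK visit.

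For an affected woman, weight-predicted CL would be off by about 10-15% at 1 SD above the median and 18-25% at 2 SD above, against about 1% with her own weight 1 kg off. These figures rest on an assumed mean of 68 kg, SD of 10 to 16 kg and exponent 0.75. They describe the prediction from weight, not her estimated CL. Per affected woman the population value moves by about 0.4-0.5% at n = 50 and about 2% at n = 12, so the effect is small unless many weights are missing. A reader might also infer that the gestational-age effect is materially biased. The direction of that worry is reasonable, but nothing in the documents allows its size to be calculated.

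**What to change.** Replace the rule for weight in the SAP's missing-data paragraph with an order of preference:

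1. At baseline, use the woman's screening value first.
2. At later visits, use her own nearest measurement, or interpolate between her adjacent ones, within the same period (pregnancy or postpartum).
3. Only if she has no usable value, use a median specific to gestational age, or a postpartum median after delivery.
4. Report how many weights were imputed, by visit and by method.

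The cost is a sentence or two in the SAP and one line in the report. No new data, visits or sample size are needed.
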